Study Protocol

TRANSFORM Heart Failure with Reduced Ejection Fraction: TRANSFORM-HFrEF (Version 1.1)

A Randomized Registry Trial to Evaluate Best Practices and Improve Adherence to Guideline Directed Medical Therapy for Heart Failure with Reduced Ejection Fraction

[name], MD FACC, FESC

Trustee, American College of Cardiology, Washington, DC

Cardiology Division, Massachusetts General Hospital

Hutter Family Professor of Medicine, Harvard Medical School

Senior Cardiometabolic Faculty, Baim Institute for Clinical Research

Boston, MA

Correspondence:

[name] MD, FACC, FESC Massachusetts General Hospital [name] P: [contact]

F: [contact] F: [contact]

E: [contact]

T: [name]

A. Study Overview

1. Purpose of the Study

The goal of the TRANSFORM-HFrEF trial will be to study the current guideline directed medical therapy (GDMT) landscape for HFrEF, and determine effective methods and models of increasing adherence to GDMT and improving Quality of Life (QOL) in outpatient settings within the context of the 20-minute visit. This will be achieved through a randomized evaluation that shifts standard clinical interview and documentation requirements outside the office visit and building the patient and physician relationship through trust and shared goal setting.

2. Background and Significance

Heart Failure (HF) is the cardiovascular epidemic of the 21st century, affecting millions of patients world-wide. It is believed that HF is the only cardiovascular diagnosis rising in incidence among elderly patients and is the #1 diagnosis leading to hospitalization among Medicare recipients. In addition to being increasingly prevalent, HF has a poor outlook after initial diagnosis and is associated with poor quality of life (QOL) in affected patients; this not only leads to burden on patients, family and other caregivers, but also on the healthcare system. For all these reasons, optimizing the understanding and care of patients with HF is a major priority.

Although clinical practice guidelines clearly articulate optimal GDMT for care of patients with HFrEF, implementation of GDMT into the management of such patients has proven to be suboptimal, with most patients under-treated relative to goal therapy.

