- Quick Tips series provides guidance on many of the topics that are raised during medical visits, but we may not have sufficient time to go into great detail about; for example, how to record daily weights, stay active, limit sodium, take medications, watch for triggers that can exacerbate heart failure, and pay attention to emotional health and mental outlook

The Usual Care arm, will be managed as close to "true" usual care as possible. To avoid influencing management, once randomized to usual care, other than to collect QOL measures (assessed using the Kansas City Cardiomyopathy Questionnaire-23) at baseline, 3 months, and 6 months, study sites will not be contacted until the study has completed and they will be unaware of allocation to usual care. They will not receive specific pre-visit guidance, and though publicly available, sites will not be specifically provided ACC tools.

B. Data Management

Participating sites submit data using an electronic health record (EHR) system integration (SI) tool, where relevant registry data fields can be extracted from a practice's EHR and is then transmitted to a secure database.

Intervention Arm

Steps include:

Data extraction: Mapped to pre-specified data fields, a data extractor (such as that provided by FIGmd) will extract the EHR data to storage at Veradigm for PINNACLE sites. FigMD has historically provided the data extractor solution for the PINNACLE Registry and provides similar services to multiple medical societies across the United States of America. Data extracted may include the following: age, sex, LVEF, medication list (including doses), and laboratory results (such as basic metabolic panel). For the purposes of the study, data from the local EHR will be extracted on a weekly basis.

Creation of Reveals: Following, a similar extractor will then process data to HealthReveal for non-PINNACLE sites, where a dashboard will be created. This dashboard will include a) lists of eligible patients for the study and b) an update on opportunities for further medication optimization. The latter information will be based on guideline-directed medical targets as articulated in the ACC 2020 Expert Consensus Decision Pathway document on management of HFrEF. The dashboard containing the reveals will be conveyed to the sites.

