KCCQ Symptom Stability Domain: measures recent changes in patients' symptoms; their shortness of breath, fatigue or swelling. It compares patients' frequency of heart failure symptoms at the time of completing the KCCQ with their frequency 2 weeks ago. As a measure of change, it is most interpretable as a baseline assessment of the stability of patients' symptoms at the start of a study and shortly thereafter, as a measure of the acute response to treatment. This domain is not included in the summary scores.

Clinical Summary Score: includes total symptom and physical function scores to correspond with New York Heart Association ("NYHA") Classification.

Overall Summary Score: includes the total symptom, physical function, social limitations and quality of life scores.

The KCCQ-23 data will be blinded and stored until end of trial.

Following completion of usual procedures, the patient will be sent home, and followed up per study protocol at 3 month intervals for up to 3 clinical visits and with as many 'as needed' visits to achieve optimal GDMT. At each visit, the Dashboard will provide updated information focused on opportunities for optimizing GDMT.

Usual Care Arm

In the Usual Care Arm, eligible patients will be identified and sites will be alerted to the roster of patients eligible for study participation. These patients will be offered participation into a study of health status in those with chronic HFrEF and if agreeable they will be consented for inclusion to the study and information recorded. Data extracted may include the following: age, sex, LVEF, medication list (including doses), and laboratory results (such as basic metabolic panel). Following, the KCCQ-23 will be recorded via Medable, as above.

To maintain "usual care" as much as possible and avoid internal contamination bias, the managing site will not be aware the medical management is being monitored and the patient will not receive CardioSmart materials.

Follow up in the Usual Care arm will be at the discretion of the managing site. KCCQ-23 will be recorded remotely via Medable over the 6 months of follow up.

Analytics

At study completion, a data extractor (such as that provided by FIGmd) will extract the EHR data from storage and a data sheet across study visits will be provided to the analytic center at the Massachusetts General Hospital.

Safeguards

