Adult patients ages 18 years and older with heart failure with Left Ventricle Ejection Fraction (LVEF) \leq 40% will be identified via an initial data extraction from interested sites. Participating sites will receive a roster of eligible patients, in order to best plan their enrollment. There will be no discrimination or bias with respect to patient inclusion on the basis of sex, race, or religion.

5. Subject Recruitment and Compensation

Upon identification of eligible patients, members of the clinical team will approach the patient with the offer to participate in a clinical study.

At **Intervention sites**, patients will be presented with the goals of the study, and given time to review the Informed Consent (prepared in their own language). Following, if the patient agrees, consent will be signed and patient included in the trial.

At **Usual Care sites**, patients will be presented with a proposal for periodic HFQoL assessment. If the patient agrees, consent will be signed and patient included in the trial.

No compensation will be offered to patients or families for participation in the registry or study.

6. Consent Process

Study consent will be provided electronically ("e-consent"), using Medable software. Consent materials will be provided with sufficient time for the patient to consider their participation in the study. For patients in the Intervention Arm of the study, consent materials will describe the study procedures, expected risks and expected benefits. For patients in the Usual Care arm, consent materials will only focus on the KCCQ-23. All consent materials will be in the patients' native language.

If the patient agrees to participation in the study, their informed consent will be recorded through e-consent processes with signature stored at Medable.

At any time, patients may withdraw consent. In such a circumstance, patients will be analyzed per intent to treat.

7. Subject's Capacity to Give Legally Effective Consent

Only those patients capable of giving informed consent will be enrolled in the study.

8. Study Interventions

In the Intervention arm, for each study visit, the site will receive a pre-visit assessment of GDMT accompanied by recommended adjustment(s) using information extracted weekly from the sites' EHR.

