The recommended adjustment(s) will be conveyed using proprietary software from HealthReveal, with a suggested follow up plan. All reminders regarding dosing targets are based on the 2020 ACC Expert Consensus Decision Pathway for Optimization of Heart Failure Treatment.

Additionally, during visits at baseline, 3 months, and 6 months, the KCCQ-23 will be completed.

In the Usual Care arm, during visits at baseline, 3 months, and 6 months, the KCCQ-23 will be completed.

9. Risk/Benefit Assessment

As study procedures reflect optimized heart failure care via guideline recommendations supported by the clinical judgment of the managing physician, there is no envisioned procedural risk to patients through involvement in the study. No testing, time, risk, or procedures beyond those required for routine care will be imposed. The primary risk associated with this project is the potential for a breach of patient confidentiality. The ACCF has established a robust plan for ensuring appropriate and commercially reasonable physical, technical, and administrative safeguards are in place to mitigate such risks as described in the Data Management section of this protocol.

10. Costs to the Subject and Compensation

There are no costs or compensation to the patient for participation in the TRANSFORM-HFrEF study.

11. Data Analysis and Statistical Considerations

Primary endpoint; compared to usual care:

From baseline to 6 months change in average composite endpoint of target dose achievement for the main classes of drugs (RASi/beta blockers/MRA/SGLT2i) among eligible patients without documented contraindications or intolerance.

Goal doses will be based on the 2020 ACC Expert Consensus Decision Pathway for Optimization of Heart Failure Treatment (4).

To calculate this composite:

Numerator = receiving ARNI/ACEI/ARB at 50% or higher of target dose + receiving evidence-based beta blocker at 50% or higher of target dose + receiving MRA at 50% or higher of target dose + receiving SGLT2i at 50% or higher of target dose.

Denominator = eligible to receive ARNI/ACEI/ARB and no documented reason for not receiving higher dose, eligible to receive evidence-based beta blocker and no documented reason for not receiving higher dose, and eligible to receive MRA and no documented reason for not receiving higher dose, and eligible to receive SGLT2i and no documented reason for not receiving higher dose.

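### The primary score is read from EHR medication data that only intervention sites are prompted to check, so list corrections may differ by arm and count as prescribing change

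*Protocol*

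**What the plan says.** **The endpoint.** Protocol section 11 defines the composite by what the patient is receiving: "Numerator = receiving ARNI/ACEI/ARB at 50% or higher of target dose + receiving evidence-based beta blocker at 50% or higher of target dose", then MRA and SGLT2i on the same rule. The score is the change from baseline to 6 months.

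**The source.** For both arms, section B (Data Management) uses the same sentence: "Data extracted may include the following: age, sex, LVEF, medication list (including doses), and laboratory results". Under Analytics in the same section, at study completion a data extractor "will extract the EHR data from storage and a data sheet across study visits will be provided to the analytic center". No dispensing, fill, dated-order or patient-confirmed source is named, and no reconciliation of the list at baseline is required in either arm.

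**The intervention.** Section 8 says that in the intervention arm "the site will receive a pre-visit assessment of GDMT accompanied by recommended adjustment(s) using information extracted weekly from the sites' EHR". Under Creation of Reveals in section B, the dashboard carries "an update on opportunities for further medication optimization". Intervention patients may also receive a Heart Failure Action Plan that covers their medications (section A.3).

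**Usual care.** Sections A.3 and B state that these sites get no pre-visit guidance and do not know that their medical management is being monitored.

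**The concern.** The EHR record that supplies the outcome is also the record fed back to sites, in one arm only. When the dashboard flags a class that the patient already takes (prescribed elsewhere, or listed at an old dose), one possible response is to correct the list. The endpoint as defined cannot tell that correction from a new prescription. The third worked example in section 11 shows the scoring: spironolactone goes from 0 to 25 mg and the patient's ratio from .000 to .33. A patient who took that drug throughout, and whose list was only put right, would score the same.

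Prompts concern classes that currently score 0, so prompted corrections would tend to be upward. Section A.2 counts medication reconciliation among the tasks competing for a 20-minute visit, so usual-care lists may be corrected less often. The planned effect is small (10% versus 5% of patients improving), so a modest difference between arms in recording could matter. The problem lies in the numerator and would remain if the set of eligible classes were fixed at baseline.

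**Working it through.** **Inputs from Protocol section 11 (power calculations).** Two-sided Wilcoxon rank-sum test at 0.05 with 90% power; 5% of patients decrease in each arm; 5% (usual care) versus 10% (intervention) increase by one point; 1280 per arm, or 1536 per arm with the loss allowance.

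**Assumed input.** *e* is the share of intervention patients who gain one class from list correction alone, net of downward corrections and in excess of usual care. The protocol gives no figure for it, so a range is shown.

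**Formulas (normal approximation with tie correction).** The categories are decrease / no change / increase.
- Usual care: 0.05 / 0.90 / 0.05. Intervention: 0.05 / (0.90 − e) / (0.05 + e).
- θ = P(intervention change > usual-care change) + ½P(equal) = 0.05×0.025 + (0.90 − e)×0.50 + (0.05 + e)×0.975 = 0.5 + 0.475e.
- Tie factor T = 1 − Σp̄³, where p̄ is the category share averaged over the arms.
- SE = √[T / (3 × 2n)], z = (θ − 0.5)/SE, rejection probability = Φ(z − 1.96) + Φ(−z − 1.96).

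**Step 1, the plan's own figure.** The planned effect is e = 0.05. Then θ − 0.5 = 0.02375 and T = 1 − (0.05³ + 0.875³ + 0.075³) = 0.3295. For 90% power the total is (1.960 + 1.282)² × 0.3295 / (3 × 0.02375²) ≈ 2046, or 1024 per arm after rounding up. The stated 1280 is not reproduced: it gives 95.2% power, and it equals 1024/0.80. That mismatch is a separate matter. The stated 1280 is used below.

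**Step 2, no prescribing effect, list correction only (n = 1280 per arm).** For e = 0.02: θ − 0.5 = 0.0095; T = 1 − (0.05³ + 0.89³ + 0.06³) = 0.2947; SE = √(0.2947/7680) = 0.00619; z = 1.53; rejection probability 0.335. Over the range:

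| Net excess e | p<0.05, 1280 per arm | p<0.05, 1536 per arm |
|---|---|---|
| 0 | 5.0% | 5.0% |
| 0.5% | 6.8% | 7.2% |
| 1% | 12.3% | 13.8% |
| 2% | 33.5% | 39.0% |
| 3% | 61.6% | 69.5% |
| 4% | 84.0% | 89.9% |
| 5% | 95.2% | 97.8% |

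Simulating the tie-corrected test (20,000 replicates, 1280 per arm) gives 5.1%, 6.8%, 12.0%, 33.7% and 61.8% for e = 0, 0.5%, 1%, 2% and 3%. At 1280 per arm the probability passes 50% near e = 2.6% and 90% near e = 4.5%. An excess of 2% is 2/5 = 40% of the planned 5-point effect.

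**Step 3, sign.** If a share u gains a class and a share d loses one through correction, both in excess of usual care, the same algebra gives θ − 0.5 = 0.475(u − d). Only the net excess matters: at u = d the shift is zero, and at d > u it runs against the intervention.

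**The case against.** A reader might infer that the intervention makes sites review their medication lists, and that correcting them raises the score as a matter of course. The protocol does not support this. Sites receive an assessment and recommendations; nothing instructs them to review or correct a list. The stated aim of a design that "shifts standard clinical interview and documentation requirements outside the office visit" concerns how the visit is used and does not say that lists become more complete. Of the patient tools described, only the Action Plan expressly covers reviewing medications, and none is said to feed the EHR. Section A.2 treats reconciliation as part of ordinary visits, so some occurs in both arms.

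Further points stand:
- Corrections can remove stopped drugs or lower a listed dose, so the sign is not fixed.
- The dashboard comes before each appointment. Some corrections could precede the baseline extraction and fall into the baseline score.
- The extraction sentence says what the data *may* include. The medication list as the only source is the best reading, not a stated rule.
- Sites are randomized, while the calculation treats patients as independent, so even its 5% reference does not describe this design.
- Using routine records for the outcome is the declared design, and the precise record and date window could be left to an analysis plan.

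The last point does not dispose of the matter. If dates are not extracted with the medication entries, no later analysis plan can separate a corrected entry from a new prescription. The other points limit how strongly the concern can be put; they do not remove the one-arm prompt.

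**Conclusion.** The concern holds as a risk of differential outcome ascertainment. Outcome data come from a record that one arm is prompted to check and the other is not, and the endpoint counts a corrected entry like a new prescription. Upward corrections are the more plausible direction because prompts fall on classes scoring 0, but neither the sign nor the size of the net effect is established by the document. The rejection rates of about 12%, 34% and 62% at net excesses of 1%, 2% and 3% show how sensitive the primary test is. They do not show that such a bias is present. They rest on no true effect, independent patients, 1280 per arm, one-class changes and the planned 5% up and 5% down background. It would go too far to conclude that a positive result must be a recording artefact. The point deserves action because prevention is cheap and must be arranged at data extraction.

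**What to change.** In Protocol section B (Data Management, both arms) and section 11 (calculation of the composite):

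1. Extract the recorded start or dose-change date with each medication entry, in the same way in both arms, and the stop date where there is one.
2. Score an entry or dose that first appears after baseline but is dated before baseline as present at baseline too. Treat a stop dated before baseline alike, so that the correction works in both directions.
3. Score without knowledge of arm.
4. Keep the list-based score, so corrected, as primary. Add a pre-specified sensitivity analysis that counts a gain or loss only when an order, dose change or stop is dated after baseline.

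Requiring a dated post-baseline order for the primary score itself is not advised: it would turn an endpoint about what patients receive into one about what is ordered, and could add its own error. The proposal works on extracted data, so it does not alert usual-care sites that medication is being followed, as a mandated reconciliation might.

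The cost is the added date information in the extract, some programming and a few sentences of text. Recorded dates may be missing or may be only the date of entry, so the correction may be incomplete. The sensitivity analysis will miss undated changes by outside prescribers, possibly unequally by arm because usual-care follow-up is left to the site.

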Using this approach, each patient may contribute to the numerator or be in the denominator 1, 2, 3 or 4 times, depending on meeting criteria and if eligible in that domain. An advantage of this composite approach is that it allows for a holistic view of all classes of drugs considered and allows for assessment not only of up-titration but also down-titration as well.

Example of a patient without contraindications:

Therapy	Initial dose	≥50% target?	Final dose	≥50% target?
Sacubitril/valsartan	24/26 mg twice daily	No	96/104 mg twice daily	Yes
Carvedilol	6.25 mg twice daily	No	12.5 mg twice daily	Yes
Spironolactone	25 mg daily	Yes	25 mg daily	Yes
	Ratio = 0 + 0 + 1/1 +1 + 1= .33		Ratio = 1 + 1 + 1/1 + 1 + 1 = 1.0	
	Relative change = 66.7%			

Example of a patient with contraindication to spironolactone (previous hyperkalemia):

Therapy	Initial dose	≥50% target?	Final dose	≥50% target?
Sacubitril/valsartan	24/26 mg twice daily	No	49/51 mg twice daily	Yes
Carvedilol	6.25 mg twice daily	No	6.25 mg twice daily	No
	Ratio = 0 + 0 /1 +1= .000		Ratio = 1 + 0/1 + 1 = .50	
	Relative change = 50.0%			

Example of a patient with no contraindication to spironolactone but not receiving it:

Therapy	Initial dose	≥50% target?	Final dose	≥50% target?
Sacubitril/valsartan	24/26 mg twice daily	No	24/26 mg twice daily	No
Carvedilol	6.25 mg twice daily	No	6.25 mg twice daily	No
Spironolactone	0	No	25 mg daily	Yes
	Ratio = 0 + 0+ 0 /1 +1 + 1 = .000		Ratio = 0 + 0 +1/1 + 1 + 1 = .33	
	Relative change = 33.0%			

In the CHAMP-HF Registry, the score at baseline was 34.7%, while at 6 months it increased nominally to 36.3% ([name], *Confidential Personal Communication, January 2019*).

Secondary endpoints; compared to usual care:

- 1) Relative change in actual achieved doses of individual classes of pivotal therapies (RASi/beta blocker/ MRA/SGLT2i).
- 2) Relative change in achievement of target doses (yes/no) of pivotal therapies (RASi/beta blocker/MRA/SGLT2i).

Exploratory, compared to usual care:

- 3) Difference in patient-reported outcome/KCCQ-23 scores from baseline to 6 months.
- 4) Rate of \geq 25%, \geq 50%, \geq 75% and 100% improvement in scores.
- 5) Among those not taking an evidence-based beta blocker, % changed to evidence-based beta blocker during course of the study.
- 6) Change in % eligible taking RASi during course of the study.
- 7) Change in % eligible taking beta blocker during course of the study.

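### The primary composite's denominator rule does not match its 50% threshold and is not locked at baseline, so documentation alone can change the score

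*Protocol*

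**What the plan says.** All of the scoring rules are in Protocol section 11 (Data Analysis and Statistical Considerations).

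- The endpoint sentence defines the change in the composite from baseline to 6 months "among eligible patients without documented contraindications or intolerance".
- The numerator gives one point per class. For the first class: "Numerator = receiving ARNI/ACEI/ARB at 50% or higher of target dose". It carries no condition on documentation.
- The denominator rule for the same class is "Denominator = eligible to receive ARNI/ACEI/ARB and no documented reason for not receiving higher dose", and the rule is repeated for beta blocker, MRA and SGLT2i.
- The text then says that "each patient may contribute to the numerator or be in the denominator 1, 2, 3 or 4 times", subject to meeting the criteria and being eligible in each domain. It does not say at what date eligibility is judged.
- Three worked examples follow. Each has the same denominator at both time points. The one dropped class rests on a reason that already existed (earlier hyperkalaemia).
- The power paragraph describes the score change as running from -3 to +3.

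The arms differ in what their clinicians see. At intervention sites (section 8), "the site will receive a pre-visit assessment of GDMT accompanied by recommended adjustment(s) using information extracted weekly", and the dashboard (section B, Creation of Reveals) carries "an update on opportunities for further medication optimization". In usual care (section B, Usual Care Arm), "the managing site will not be aware the medical management is being monitored".

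**The concern.** There are two linked faults in the formula.

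**Mismatch.** The endpoint sentence, the numerator and the denominator use three different criteria: contraindication or intolerance; 50% of target; and any recorded reason for not going higher. The third is the widest. Read literally, it could take in a patient's preference or a note that the patient is stable. It also bites on classes that already meet the numerator's threshold.

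**Unlocked denominator.** The endpoint is a change score. If class eligibility is re-read at 6 months, a reason charted after randomisation changes the score by itself, and the primary comparison is then conditioned on a post-randomisation variable. The arms may differ on that variable. Intervention clinicians are repeatedly shown titration gaps and recommended adjustments, and a titration attempt that fails tends to leave a recorded reason. Usual-care clinicians are shown nothing.

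What is at stake is whether a difference in the primary endpoint can be read as a difference in prescribing.

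**Working it through.** **1. The plan's own figures.** Ratio = classes at 50% of target or more, divided by eligible classes. The three examples give 1/3 to 3/3 (change 66.7 points), 0/2 to 1/2 (50.0) and 0/3 to 1/3 (33.3, printed as 33.0). They reproduce, with a constant denominator each time.

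**2. The mismatch.** Take three eligible classes, two of them at 50% of target or more. One of those two is at 50-99% with a recorded reason for not going higher that is not a contraindication or intolerance.

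- By the endpoint sentence the class stays in: 2/3.
- By the denominator rule, with the numerator as worded: 2/2.
- By the denominator rule, with the numerator restricted to the same classes: 1/2.

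One patient on fixed treatment has three possible scores.

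**3. Charting alone, if the denominator is re-read at 6 months.** A reason is newly recorded for one class below 50% of target, and no dose changes:

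- 1/4 to 1/3: +8.3 points
- 2/4 to 2/3: +16.7 points
- 3/4 to 3/3: +25 points
- 0/4 to 0/3: no change

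Stopping one of two at-goal classes with a recorded reason gives 2/4 to 1/3 instead of 2/4 to 1/4, so down-titration is under-counted. With a denominator fixed at baseline, charting alone changes every one of these scores by zero.

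**4. Effect on the planned test.** Inputs from the power paragraph: 5% of patients fall and 5% rise in usual care, two-sided Wilcoxon rank-sum test at 0.05, 1280 per arm (N = 2560). Assumption, not in the documents: the intervention arm has an excess x of patients whose score rises through documentation only, so its -1/0/+1 shares are 5%, 90% - x and 5% + x. Prescribing is identical in the two arms.

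P(I > U) - P(I < U) = 0.95x, so the rank effect is θ - 0.5 = 0.475x. With p̄ the average share per category, z = 0.475x · √[3N / (1 - Σp̄³)], and the rejection probability is about Φ(z - 1.96).

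| Assumed excess x | 1 - Σp̄³ | z | Rejects |
|---|---|---|---|
| 1 per 100 | 0.2828 | 0.783 | about 12% |
| 2 per 100 | 0.2947 | 1.534 | about 34% |
| 3 per 100 | 0.3064 | 2.256 | about 62% |
| 5 per 100 | 0.3295 | 3.626 | about 95% |

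Simulation with 20,000 trials agrees, and gives 4.9% at zero excess. The last row is simply the power of 1280 per arm for the planned 5% versus 10%.

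**5. Cross-check on the ratio scale.** Assumptions: four eligible classes, each at goal independently with probability 0.347 (the CHAMP-HF baseline score quoted in section 11); 5% up and 5% down in both arms; and a share d of unmet classes gaining a recorded reason in the intervention arm only. In 800 simulated trials per value, the test rejects in about 25% (d = 1%), 70% (2%) and 94% (3%), against 5.75% at d = 0. On the pooled score, 0.347 / (1 - 0.653d) gives 35.9% at d = 5%. At d = 6.7% it gives 36.3%, which is the whole 6-month drift quoted for CHAMP-HF.

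**The case against.** The strongest reply is that the protocol nowhere says eligibility is re-read. All three examples hold the denominator constant, so a baseline-fixed rule fits the text at least as well, and under that rule charting has no effect. This is fair as far as it goes. But no example shows a reason arising during follow-up, so the examples do not settle the rule, and they do not touch the threshold mismatch.

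A reader might infer that the intervention itself prompts charting. The documents do not support that. They describe prompts to adjust therapy, not to record a reason; the illustrative list of extracted data names no field for reasons; and usual-care clinicians may chart reasons in routine practice.

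A reader might also infer that the ratio will exceed 1, for example 3/2. That follows only if the numerator is counted without regard to eligibility. The sentence on contributing up to four times is qualified by eligibility in each domain, which favours restricting the numerator. In that case a success is deleted instead, and the score can fall. The bias is therefore not one-directional.

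The rejection rates rest on an assumed excess and on independent patients, although sites are randomised. They also use the power paragraph's scale. If the score is a pure count of classes at goal, as the -3 to +3 range suggests, charting cannot move it. That stands as a limit on the size. It also exposes a conflict with the ratio defined just before it in section 11.

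Finally, the secondary endpoints on achieved doses and target achievement by class state no documented-reason exclusion, so a charting artefact might show up as a primary gain without matching dose changes. That helps interpretation but does not repair the primary endpoint.

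**Conclusion.** The point holds as a defect in how the primary endpoint is defined. The mismatch between the 50% threshold and the higher-dose exclusion is on the page and needs no assumption about behaviour. The unlocked denominator is an ambiguity with a serious consequence under one reading. A documentation-only rise needs three things: a 6-month re-read, a class below 50% of target, and another class at goal.

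Under those conditions, and with the excess assumed, 1 to 3 extra patients per 100 would give rejection in about 12% to 62% of trials with no prescribing effect, against a planned difference of 5 per 100. The documents do not establish that such an excess will occur or that the intervention is built to cause it. They show only that it is plausible, through the recommended adjustments and failed titration attempts.

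**What to change.** In section 11:

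1. Define each patient's eligible classes once, from the baseline extract (data up to enrolment), and use them at both time points. Enrolment is a workable anchor in both arms; release of the allocation is not, because usual-care sites are never told theirs.
2. Count the numerator only within those classes.
3. Replace the higher-dose exclusion with a documented contraindication or intolerance that prevents reaching the 50% threshold, and use the same wording in the endpoint sentence.
4. State whether the analysed score is the ratio or a count, and reconcile this with the -3 to +3 range.
5. Keep the time-varying denominator as a sensitivity analysis, and tabulate newly documented reasons by arm.

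The cost is mainly endpoint wording, and the fixed denominator agrees with all three worked examples. Because no field for reasons is named among the extracted data, the sponsor should confirm that reasons can be extracted in both arms. The downside is that intolerance first found during follow-up counts as not at goal, possibly more often in the intervention arm. That is conservative for the intervention, and the sensitivity analysis will show it.
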